3.8. Appropriateness of Safety Measurements

The safety assessments in the study are standard safety measures in clinical trials.

4. STATISTICAL METHODS

4.1. General Considerations for Data Analysis

The focus of the statistical analysis will be the comparison with controls of the photoallergic response to the study products. The diagnosis of photosensitization response will be made by the Investigator based on review of the observed skin responses after Challenge.

The mean score by subject and treatment, including all scores assigned during Induction, will be analyzed in the analysis of variance with factors subject and treatment. All pairwise treatment comparisons will be performed.

All statistical processing will be performed using the SAS® system (version 9.2 or higher). No interim or subgroup analyses are planned.

4.2. Sample Size and Power Considerations

The sample size of 50 evaluable subjects conforms to industry and regulatory standards for determination of irritation/sensitization when topical application to skin is followed by light exposure.

4.3. Subject Populations for Analysis

All subjects who receive treatment will be evaluable for AEs. The evaluation of photosensitization will be based on all subjects who complete the Challenge Phase of the study. Subjects who completed Challenge are those who have received at least 6 applications/irradiation of study products, and at least 11 subsequent evaluations during Induction, completed the Rest Phase and have received one application of study products at Challenge, subsequent irradiation and at least 4 evaluations (3 post-irradiation evaluations) for that product. The analysis of local tolerability (photo irritation) will be based off all subjects who complete the Induction Phase of the study. Subjects who completed Induction are those who have received at least 6 applications/irradiation of study products, and at least 11 subsequent evaluations during Induction.

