3. INVESTIGATIONAL PLAN

3.1. Study Design

This will be a randomized, double-blind, single-center, vehicle-controlled, within-subject comparison study of the study products, CCP-020 (Diacerein 1%) topical ointment, vehicle ointment, and an untreated irradiated non-occluded (open) control site. A total of 4 application sites (2 cm x 2 cm each) will be marked on the subject's back and distributed so that 2 sites are on each side of the back. One side of the back will be designated for irradiation after approximately 24 hours (± 4 hours) of study product application and the other side will remain non-irradiated. An additional site will be marked on the "irradiated side" of the back. The site will receive no study product, but will be irradiated at Challenge to serve as an untreated irradiated non-occluded control.

A defined area (approximately 50 cm²) on the infrascapular region of each subject's back will be irradiated to determine the minimal erythema dose (MED) of ultraviolet (UV) light.

During the 3-week Induction Phase, 0.2 mL of each study product will be applied to 2 sites twice each week (Monday and Thursday) for approximately 24 hours (± 4 hours) under occlusive patch conditions (6 applications). After patch removal, all application sites will be evaluated and one application site of each study product will be irradiated with 2 times the subject's MED using the full Xenon lamp spectrum. The sites will be evaluated by a trained evaluator. All sites will be reevaluated post irradiation, at approximately 48 hours later when irradiated on Tuesdays and at approximately 72 hours later when irradiated on Fridays except when irradiated on the last Friday of the Induction Phase or if a subject is taking a missed visit during induction, the sites will not be evaluated. These procedures will be performed each week for 3 weeks of the Induction Phase. Dermal reactions at the application sites will be evaluated using a visual scale that rates the degree of erythema, edema, and other signs of cutaneous irritation (see [Table 3](#) and [Table 4](#)).

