At the end of the Induction Phase, the subjects will enter a Rest Period of 10-17 days and then a Challenge Phase. One application/irradiation session may be missed during the Induction Phase. It must be made-up during Week 4. An additional application of study product may be applied on the Monday of rest week 4 if the subject had missed an irradiation session during the induction phase of the study. In either case, no evaluation will be required following irradiation.

At Challenge, each study product will be applied in an amount of 0.2 mL to 2 naive sites once for approximately 24 hours (± 4 hours) under occlusive patches. After 24 hours (± 4 hour) of product application, all sites will be evaluated and one application site of each product and the additional untreated control site will be irradiated. The sites will be examined for dermal reactions at approximately 24 hours (± 4 hours), 48 hours (± 4 hours), and 72 hours (± 4 hours) post-irradiation. A Rechallenge will be performed if a cutaneous response observed during the Challenge Phase indicates possible photosensitization or at the discretion of the Investigator.

The safety endpoints for this study are irritation responses during the Induction Phase, positive responses at Challenge (i.e., reactions indicative of a sensitization response) and adverse events.

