3.3.3. Interruption or Discontinuation of Treatment

A reaction of at least moderate erythema (2) accompanied with mild, but definite edema (1) to a study product observed after the first patch application/irradiation sequences of the Induction Phase may indicate the subject to be pre-sensitized, and may cause the discontinuation of the subject from the study.

After the second reading of the Induction Phase, either of the following conditions will require the study product be applied to a naive patch site under semi-occlusive patch conditions:

- Reaction of >50% “p” or “p” with no erythema, minimal/doubtful erythema, or definite erythema; or “D” (see [Tables 3 and 4](#));
- Any reaction of definite erythema with definite edema.

Study product may not be relocated more than twice.

The 3 weeks of continuous patch contact during the Induction Phase frequently results in tape-related irritation that is exacerbated by warm weather, but which occurs among some individuals irrespective of the season. Tape-related irritation will not be graded as a photosensitivity response at the patch site, but will be noted separately on the CRF. Severe tape-related irritation will necessitate a change in the application site. As above, the application site will only be changed twice and then the subject must be discontinued.

One application/irradiation session may be missed during the Induction Phase. It must be made-up during Week 4. In this case, no evaluation will be required following irradiation. Only one missed patch application for study product is allowed. A subject must be discontinued and considered not complete if more than one application is missed.

In accordance with legal requirements and ICH-GCP guidelines, every subject or his/her legal representative has the right to refuse further participation in the study at any time and without providing reasons (see also [Section 5.3](#)). A subject's participation is to be terminated immediately upon his/her request. The Investigator should seek to obtain the reason and record this on the case report form (CRF).

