3.5.2. Visit Schedule

A summary of the visit schedule and assessments is presented in [Table 2](#).

Table 2: Visit Schedule and Assessments

	Screening	Day 1 ^a (M)	Induction				Rest	Challenge (Week 6)				
			M 8, 15	Tu 2, 9, 16	Th 4, 11, 18	F 5. 12, 19		Week 4 & 5	M	Tu	W	Th
Informed consent	X											
Inclusion/Exclusion	X	X										
Medical history	X											
Demographic information	X											
Fitzpatrick Skin Typing	X											
UPT		X										X
MED irradiation/evaluation		X ^b										
Randomization		X										
Product application		X	X		X			X				
Application site evaluations			X ^c	X	X	X ^d			X	X	X	X
Application site irradiation				X		X ^d		X	X			
Make-up evaluation/application							X ^e					
Make-up evaluation/irradiation							X ^e					
Review of concomitant medications	X	X	X	X	X	X	X ^f	X	X	X	X	X
Review of AEs	X	X	X	X	X	X	X ^f	X	X	X	X	X

a Screening and the first day of Induction (Day 1) may take place on the same day.

b MED irradiation on Day 1 and MED evaluation on Day 2.

c The first Monday (Week 1) of the Induction Phase.

d Evaluations will not be conducted after irradiation on the last Friday of the Induction Phase. Untreated control site will also be irradiated.

e Make-up evaluation/application and evaluation/irradiation are performed as necessary (see [Section 3.5.1](#)).

f Concomitant medications and AEs will be reviewed only for subjects who are required to return to the test facility for make-up visits during Rest Period - Week 4.

Note: The visit schedule may be revised if necessary.

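### A subject with a positive Challenge reaction who then misses one reading is left out of the photosensitization incidence

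*Combined protocol and SAP*

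**What the plan says.** Section 4.3 defines the analysis set: "The evaluation of photosensitization will be based on all subjects who complete the Challenge Phase of the study". Such a subject has at least 6 applications/irradiations and 11 evaluations in Induction, has completed the Rest Phase, and at Challenge has one application, "subsequent irradiation and at least 4 evaluations (3 post-irradiation evaluations) for that product". The section makes no exception for a subject who has already reacted.

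Section 3.1 names among the safety endpoints "positive responses at Challenge (i.e., reactions indicative of a sensitization response) and adverse events". Under section 4.1 the Investigator makes the diagnosis "based on review of the observed skin responses after Challenge". Section 4.6.2 reports incidence by treatment and calculates a 95% confidence interval if photosensitization occurs.

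For Induction, section 4.3 says: "The analysis of local tolerability (photo irritation) will be based off all subjects who complete the Induction Phase of the study". Sections 3.6.1 and 3.6.6 state that a response gradable with Table 3 or Table 4 is not an adverse event.

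**The concern.** The study exists to find out whether the ointment can cause a photoallergic reaction, and the count of positive Challenge responses answers that question. A completer rule normally protects against calling a subject negative on too little follow-up. Here it also removes a subject in whom the event has already been seen. With 50 evaluable subjects, one case is the difference between a zero result and a non-zero one. Section 3.3.1 enrols until 50 have completed, so a removed reactor does not lower the reported denominator.

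**Working it through.** **Step 1: required against scheduled Challenge readings.**

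- Required (section 4.3): 4 evaluations, 3 of them post-irradiation.
- Scheduled (section 3.5.1, Challenge): 1 at patch removal + 3 post-irradiation (24, 48, 72 hours) = 4. Section 3.1 gives the same times.
- Post-irradiation readings a subject may miss: 3 − 3 = 0.

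Section 3.5.1 also has a baseline look before the Challenge patch. Counting it would give 5 readings against 4 required, but the separate requirement of 3 post-irradiation readings still allows no miss.

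**Step 2: does other text return the subject to the set?** Sections 4.1 and 4.6.2 say who diagnoses and on what basis, not which subjects enter the incidence. Section 3.5.1 provides for Rechallenge but does not change the population. Section 4.6.1 tabulates scores, not diagnosed cases. None restores the subject.

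**Step 3: how often a subject could be lost this way.** The documents give no missed-reading rate. Assume each of the three readings is missed independently with probability m. The chance of missing at least one is 1 − (1 − m)³:

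- m = 1%: 3.0%
- m = 2%: 5.9%
- m = 5%: 14.3%

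**Step 4: direction of bias.** Let p be the true rate, r the chance that a reactor misses a reading, and q the chance for a non-reactor. The rate expected among completers is p(1 − r) / [p(1 − r) + (1 − p)(1 − q)]. If r = q, this equals p and there is no bias. If r > q, it is below p.

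**Step 5: illustration.** Take 50 completers with no case, and add k challenged non-completers with at least one post-irradiation reading, x of whom are diagnosed. Both k and x are assumed. The incidence is x / (50 + k). The exact (Clopper-Pearson) limits are the 2.5% point of Beta(x, n − x + 1) and the 97.5% point of Beta(x + 1, n − x). The plan names no interval method, so this one is an assumption.

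| x | k | Incidence | Exact 95% CI |
|---|---|---|---|
| 0 | 0 | 0/50 = 0% | 0 to 7.1% |
| 1 | 1 | 1/51 = 2.0% | 0.05% to 10.4% |
| 1 | 2 | 1/52 = 1.9% | 0.05% to 10.3% |
| 2 | 2 | 2/52 = 3.8% | 0.5% to 13.2% |

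In every row the plan as written reports 0/50. Section 4.6.2 calls for an interval only when a case occurs, so the 7.1% upper limit would not be planned output either.

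**The case against.** There is a diagnostic reason to want all three readings. Section 3.5.7.1 treats a reaction that grows over time as further support for photosensitivity, and a subject with only a 24-hour reading cannot show that. A suspected reactor may also go to Rechallenge, which has its own full set of readings. This stands as a reason to keep the completer count. It does not justify having no other count, because section 3.5.7.1 treats growth over time as supporting evidence, not as a requirement.

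The investigator might report such a case anyway. That would mean departing from the written population after the reaction was known. Section 3.4.5.2 mentions a Statistical Analysis Plan still to be finalized. It may address this, but no separate text is in the documents.

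A reader might go further and infer that photosensitized subjects are also lost during Induction, unseen by any analysis. The documents do not support that, for four reasons:

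- The diagnosis rests on Challenge. Induction sites are "irradiated with 2 times the subject's MED using the full Xenon lamp spectrum", so a reaction there may be irritation. These exits are undiagnosed.
- The exit tied to a specific product reaction in section 3.3.3 follows the first sequence. Such a reaction "may indicate the subject to be pre-sensitized, and may cause the discontinuation of the subject from the study". Keeping it out of a count of newly induced sensitization is reasonable.
- After the second Induction reading, section 3.3.3 moves the product to a naive site for the stronger reactions it lists, up to twice. These subjects are not removed at once.
- Section 4.6.1 plans frequency counts of all scores from both phases and names no completer restriction, so the scores of subjects who left may well be shown.

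Nor does the point rest on the Induction reading count. Table 2 can be read as giving 2 + 3 + 3 + 3 = 11 readings (Mondays, Tuesdays, Thursdays, Fridays) against 11 required. But the table also lists make-up evaluations in Week 4, footnote c does not fit its column, and section 3.5.7.1 describes other reading times.

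What remains for Induction is a reporting gap. Section 4.6.1 does not state its population, and discontinuation for a gradable site reaction appears in neither the adverse event tables nor any summary planned in section 4.

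**Conclusion.** The point holds for Challenge. As written, the plan leaves out of the photosensitization incidence a subject already observed with a positive reaction who misses one post-irradiation reading. This follows from the text and needs no assumption.

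Its size is unknown. The figures above rest on assumed numbers of non-completers and cases, an assumed missed-reading rate, and a chosen interval method. They show that one or two subjects would matter at this sample size, not that any will be lost.

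A reader might infer that a result of 0/50 would be biased. That goes too far. There is bias toward zero only if reactors miss readings more often than non-reactors. If missing is unrelated to the reaction, the rate is unbiased, but an observed positive response is still left out of the count.

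**What to change.** **Section 4.3, main change.** Keep the completer count. Beside it, for each product, give the incidence and exact 95% CI, whether or not a case occurs, in all subjects who had the Challenge application, the Challenge irradiation and at least one post-irradiation reading. Include them whether or not they reacted: adding only non-completers who reacted would select the denominator on the outcome. The Investigator diagnoses while blinded, from the readings available and from Rechallenge if it was done. If both the irradiated and the non-irradiated site of a product reacted and there was no Rechallenge, the subject stays in the denominator and is listed as suspected, unconfirmed, because section 3.5.7.1 compares the two sites at Rechallenge.

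**Section 4.6.1, secondary change.** State that the score frequency counts use all treated subjects. List, by product and irradiation status, any subject discontinued for a test-site reaction. None of these is counted as photosensitized.

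**Cost.** A short paragraph, one phrase and one extra table or listing, with no added visits, readings or subjects. The second figure may be less favourable, and some diagnoses will rest on incomplete readings. A non-reactor with only an early reading counts as negative although a late reaction could have been missed, which is a further reason to show both figures.

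### The 11-reading Induction requirement in section 4.3 has no slack, so a subject who uses the permitted Week 4 make-up can, on several readings of the protocol, be left out of the photosensitization count

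*Combined protocol and SAP*

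**What the plan says.** Section 4.3 defines the analysis sets. For the main outcome: "The evaluation of photosensitization will be based on all subjects who complete the Challenge Phase of the study". Challenge completers and Induction completers (the latter form the local tolerability set) must both be "those who have received at least 6 applications/irradiation of study products, and at least 11 subsequent evaluations during Induction". The Challenge set also needs the rest phase, one Challenge application, irradiation and at least four readings.

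Section 3.1 gives the reading schedule. Each application carries a reading at patch removal ("under occlusive patch conditions (6 applications). After patch removal, all application sites will be evaluated"), and a further reading follows irradiation, "at approximately 48 hours later when irradiated on Tuesdays and at approximately 72 hours later when irradiated on Fridays". The last session is an exception. Table 2, footnote d: "Evaluations will not be conducted after irradiation on the last Friday of the Induction Phase".

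Sections 3.1, 3.3.3 and 3.5.1 allow one session to be missed and require it to be made up in Week 4. Section 3.3.3 adds "Only one missed patch application for study product is allowed", and classes a subject as not complete only when more than one application is missed.

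On readings at the make-up, the text varies by place:

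- Section 3.1, in the Induction paragraph: "if a subject is taking a missed visit during induction, the sites will not be evaluated".
- Section 3.1, in the paragraph on the Rest Period: "In either case, no evaluation will be required following irradiation". Section 3.3.3 says the same in substance.
- Section 3.5.1 calls for a reading just before every application.
- Table 2, in its Rest column for Weeks 4 and 5, lists one make-up evaluation paired with the application and one paired with the irradiation. Footnote e says these are done as needed.

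**The concern.** The make-up provision exists to keep subjects in the study after one missed session. The evaluability rule can take the same subjects out of the analysis, and section 4.3 has no exception for them. Section 3.3.3 implies that a subject with one missed and made-up application is complete, while section 4.3 may say otherwise.

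The condition is also poorly matched to the outcome. Under section 4.6.2, photosensitization is judged from Challenge, with Rechallenge if needed. Sensitizing exposure comes from the six applications and irradiations. A missing Induction irritation score changes neither.

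If a make-up subject reacted at Challenge, whether that reaction entered the incidence would depend on which passage the site followed and how the phrase limiting readings to Induction was later interpreted. That decision could be taken after the reaction had been seen.

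**Working it through.** **Step 1. Reproduce the plan's figure.** The inputs are the six applications in section 3.1 and the day numbers in Table 2.

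- Patch-removal readings: Days 2, 5, 9, 12, 16, 19 = 6.
- Post-irradiation readings: Days 4, 11, 18 (48 hours after the three Tuesdays) and Days 8, 15 (72 hours after the first two Fridays) = 5. There is none after Day 19.
- Total: 6 + 5 = 11, equal to the section 4.3 minimum.

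As a cross-check, Table 2 shows 2 Mondays + 3 Tuesdays + 3 Thursdays + 3 Fridays = 11 Induction visits after Day 1. The pre-application readings on Days 4, 8, 11, 15 and 18 fall at the same visits as the post-irradiation readings and add nothing. The Day 1 baseline precedes the first application, so it is not a subsequent evaluation. Section 3.5.7.1 mentions readings at 24, 48 and 72 hours for both phases, but Table 2 has no Wednesday or weekend Induction visit for the extra ones.

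**Step 2. Count for a make-up subject.** Readings = 11 − readings lost + Week 4 readings taken and counted. The make-up application is on the Monday of Week 4 (Day 22), with removal and irradiation on Tuesday (Day 23).

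| What was missed | Lost | No Week 4 reading counted | Day 23 removal reading only | Days 22 and 23 |
|---|---|---|---|---|
| Both visits of one of sessions 2 to 6 (e.g. Days 8 and 9) | 2 | 9 | 10 | 11 |
| Only the removal/irradiation visit of a session | 1 | 10 | 11 | 12 |
| Session 6, with the Day 18 reading still taken | 1 | 10 | 11 | 12 |

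If one instead charges a missed session 1 to 5 with its own removal and post-irradiation readings, the loss is again 2 and the counts are 9, 10 and 11.

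**Step 3. Which column applies?**

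- No Week 4 reading counted: this follows if the first section 3.1 sentence bars all make-up readings, or if Week 4, which section 3.5.1 and Table 2 place in the Rest Period, is not part of Induction. The count is 9 or 10 and the subject fails in every row.
- Day 23 only: this follows if the removal reading is taken but no pre-application reading is taken or counted. The count is 10 (fails) or 11 (passes).
- Both days: this follows from Table 2's two make-up rows and the pre-application rule in section 3.5.1, provided that Week 4 counts. The count is 11 or 12 and the subject passes.

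**Step 4. Effect on the reported result.** Section 4.6.2 calculates a 95% interval only if photosensitization occurs. The plan names no method; assume an exact (Clopper–Pearson) interval and, for illustration, 50 evaluable subjects.

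- 1 reaction in 50: 1/50 = 2.0%, interval 0.05% to 10.6%.
- 0 in 50: 0%, with no interval planned. The upper bound would be 1 − 0.025^(1/50) = 7.1%.

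If the only reactor were an excluded make-up subject, the report would move from the first line to the second.

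**The case against.** The strongest reply is that the documents already rescue the make-up subject. Table 2 schedules two make-up evaluations, and section 3.5.1 requires a reading before each application. Both readings come before the make-up irradiation, so they do not conflict with the waiver of a reading after it. The broader sentence in section 3.1 is written as an exception to the 48- and 72-hour re-evaluation and can be confined to that. Footnote d does not clearly bar a Day 22 reading: it concerns evaluation after the last Friday's irradiation, and if session 6 was the one missed, that irradiation did not take place. On this view the subject reaches 11.

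This stands as one reasonable interpretation. It does not settle the matter, because the section 3.1 sentence can also be taken at face value and section 4.3 never says that Week 4 readings count as Induction readings.

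Three further points limit the consequences. Section 3.3.1 enrols until there are 50 evaluable completers, so the target number is protected. Section 4.6.1 tabulates all assigned scores, with no completer restriction stated there, so a Challenge reaction need not vanish from the report even if the section 4.6.2 incidence omits it. Requiring Induction readings is also a recognisable per-protocol choice, and those readings serve the pre-sensitization and relocation rules in section 3.3.3. All three are fair, but none makes the main analysis set determinate.

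A reader might infer that every make-up subject is excluded, or that the outcome is the same whichever session is missed. The table above shows neither is so.

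**Conclusion.** The concern holds in conditional form. The threshold of 11 equals the scheduled maximum, and a permitted make-up leaves 9 to 12 readings. A subject who missed both visits of one of sessions 2 to 6 qualifies only if both Week 4 readings are taken and counted. A subject who lost one reading qualifies if at least one is. If Week 4 readings do not count, no make-up subject qualifies.

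The defect is more than missing detail: a stated evaluability rule conflicts, on plausible readings, with a stated permitted pathway, and the set for the study's main objective is then open to interpretation. The same indeterminacy affects the local tolerability set.

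The number of subjects affected cannot be given. The documents state no make-up rate, and not every make-up subject would fail. The count rests on the six-application calendar of section 3.1 and Table 2, and on excluding the Day 1 baseline.

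**What to change.** 1. In section 4.3, define the photosensitization set by six applications/irradiations (stating that a Week 4 make-up counts toward the six), the rest period, and the Challenge application, irradiation and readings. Remove the 11-reading Induction condition from this set.
2. For the local tolerability set, either state that Week 4 make-up readings count toward the threshold or choose a threshold that make-up subjects can meet.
3. Reconcile sections 3.1, 3.3.3, 3.5.1, Table 2 (footnotes d and e) and 4.3 on which readings are taken at a make-up. While doing so, reconcile two items in section 3.5.1: its mention of 4 patch applications against 6 in sections 3.1 and 4.3, and its sentence that places a waived reading in the challenge period.

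Settle this before the first make-up visit if possible, and before unblinding at the latest.

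The cost is wording. No visit is added, since make-up subjects already attend for application and irradiation. The small downside is that some subjects in the photosensitization set may have fewer Induction irritation readings than others.

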3.3. Study Population

3.3.1. Subject Population

A sufficient number of subjects will be enrolled in order to provide 50 completed subjects evaluable for analysis; an individual subject will be allowed to participate in the study one time only.

A rationale for the choice of sample size is provided in [Section 4.2](#) of this protocol.

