4.6.2. Photosensitivity

The determination of dermal photosensitization potential will be made by the Investigator based on specific scoring criteria derived from observations in the Challenge Phase of the study and confirmed in the Rechallenge Phase, if necessary. The incidence of photosensitization reactions will be summarized by frequency counts for each treatment. If photosensitization occurs, the 95% confidence interval for the proportion of subjects with photosensitization for each product will be calculated. Photosensitivity will not be determined by statistical methods.

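### Section 4.3 leaves a subject diagnosed as photosensitized out of the reported incidence if a post-irradiation Challenge reading is missing or Induction evaluations fall short of 11

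*Combined protocol and SAP*

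**What the plan says.** Section 4.3 defines the population: "The evaluation of photosensitization will be based on all subjects who complete the Challenge Phase of the study". For Induction, a completer needs "at least 6 applications/irradiation of study products, and at least 11 subsequent evaluations during Induction". The subject must then finish the Rest Phase and, at Challenge, must "have received one application of study products at Challenge, subsequent irradiation and at least 4 evaluations (3 post-irradiation evaluations) for that product".

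Section 4.6.2 defines the outcome: "The incidence of photosensitization reactions will be summarized by frequency counts for each treatment". It adds a 95% confidence interval for each product, but only if photosensitization occurs. It names no population of its own, so Section 4.3 governs. The diagnosis is the Investigator's, from the Challenge responses and, where needed, Rechallenge (Sections 4.1 and 4.6.2).

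On numbers, Section 3.3.1 says: "A sufficient number of subjects will be enrolled in order to provide 50 completed subjects evaluable for analysis". Photoallergic potential is the study objective (Section 2), and positive responses at Challenge are a named safety endpoint (Section 3.1).

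**The concern.** The completeness rule treats positive and negative subjects alike. A full series of readings is needed before a subject can be called negative, because a reaction may appear late. A subject whom the Investigator has already diagnosed as photosensitized is in a different position. The finding exists, and a missing 72 h reading or a tenth rather than an eleventh Induction evaluation does not undo it. Section 4.3 nevertheless removes that subject from both numerator and denominator.

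The study has about 50 evaluable subjects and one question, so a single case can decide whether the report says none or some.

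**Working it through.** **1. Are the minimums the same as the schedule?**

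*Induction.* Section 3.1 gives six applications, on Mondays and Thursdays for three weeks. Each is followed by a reading at removal: "After patch removal, all application sites will be evaluated and one application site of each study product will be irradiated". Re-readings follow about 48 h after Tuesday irradiation and 72 h after Friday irradiation, with none after the last Friday.

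- Removal readings: Days 2, 5, 9, 12, 16, 19 = 6
- Re-readings: Days 4, 8, 11, 15, 18 = 5 (three at 48 h, two at 72 h)
- Total: 6 + 5 = 11

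The visit days in Table 2 agree: Monday 2 + Tuesday 3 + Thursday 3 + Friday 3 = 11. The plan's figure of 11 is reproduced and equals the full calendar count.

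*Challenge.* Removal 1 + post-irradiation 3 (24, 48, 72 h) = 4. The plan's figure of 4 is also reproduced. Section 3.5.1 adds a baseline look before application. Even if that look counted toward the 4, all three post-irradiation readings would still be required.

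*Qualifications.*
- A subject who misses a whole session after the first keeps 11 − 2 = 9 scheduled readings. Table 2 lists two Week 4 make-up evaluations. The total is 11 if both count, 10 if one counts and 9 if neither does. Section 4.3 does not say which applies.
- Section 3.5.7.1 gives 24, 48 and 72 h readings for both phases, which conflicts with Section 3.1 and Table 2 for Induction.
- Section 3.5.1 describes Induction as four applications, against six in Section 3.1. It also says that no evaluation is required after the final irradiation of the challenge period, against the 24, 48 and 72 h readings elsewhere. These passages must be reconciled. The counts above follow Section 3.1 and Table 2.

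**2. Does any other provision return a diagnosed subject to the incidence?**

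| Route | What it does |
|---|---|
| Section 4.6.2, incidence and interval | Names no other population |
| Rechallenge (Sections 3.5.1, 4.6.2) | May confirm the reaction; nothing says it restores evaluability |
| Adverse events, all treated subjects (Section 4.3) | Patch-site responses that Tables 3 and 4 can denote are not adverse events (Sections 3.6.1, 3.6.2.1, 3.6.6) |
| Section 4.6.1, assigned scores by time point | Names no population; the raw score may appear, the diagnosis would not be in the incidence |

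None does.

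**3. Effect of one omitted case**

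Leaving out one positive changes (x + 1)/(n + 1) into x/n, which is smaller whenever x < n. The exact (Clopper-Pearson) 95% limits are: lower = Beta quantile 0.025 with parameters (x, n − x + 1); upper = Beta quantile 0.975 with parameters (x + 1, n − x). For x = 0 the upper limit is 1 − 0.025^(1/n), so 1 − 0.025^(1/50) = 7.1%.

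Assume 50 other completers, none positive:

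| Case | Proportion | Exact 95% CI |
|---|---|---|
| As written, one or two positives omitted | 0/50 = 0% | upper limit 7.1%; not calculated under Section 4.6.2 |
| One positive counted | 1/51 = 2.0% | 0.05% to 10.4% |
| Two positives counted | 2/52 = 3.8% | 0.5% to 13.2% |

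**4. How often might it happen?**

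The documents give no rate of missed readings. As an illustration, assume each reading is missed independently with probability m. A subject positive at 24 h loses the 48 or 72 h reading with probability 1 − (1 − m)^2. Any subject fails the full set of 11 + 4 = 15 readings, without make-up, with probability 1 − (1 − m)^15.

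| m | 48 or 72 h lost | Any of 15 lost |
|---|---|---|
| 0.5% | 1.0% | 7.2% |
| 1% | 2.0% | 14.0% |
| 2% | 4.0% | 26.1% |
| 3% | 5.9% | 36.7% |
| 5% | 9.8% | 53.7% |

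**The case against.** Serial readings also serve the diagnosis of a positive. Under Section 3.5.7.1, erythema with edema only makes a reaction suspect, and rising intensity over time supports the diagnosis. If both the irradiated and non-irradiated sites react, a Rechallenge comparison is needed. This stands, and it is why the point is confined to subjects whom the Investigator has diagnosed, not everyone with an early reaction.

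The documents also contain mitigations. Sections 3.3.3 and 3.3.4 ask for all efforts at a final evaluation after withdrawal, Rechallenge is provided for, and raw scores may be visible under Section 4.6.1. Section 3.4.5.2 mentions an SAP still to be finalized, and its population definitions, if separate, are not known. These lower the chance of a loss or make it easier to notice. They do not put the subject into the Section 4.6.2 incidence.

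A reader might infer more than the documents support:

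- *That a reactor who receives treatment is excluded.* Section 4.3 lists no such condition. Only an unmet application, irradiation, Rest Phase or reading requirement excludes.
- *That strong reactors are the likeliest to drop out.* This is plausible but not documented. Patches are off before Challenge irradiation, so only reading visits remain.
- *That an excluded positive is replaced.* Section 3.3.1 sets a target of 50 completers and states no replacement rule.
- *That every scheduled Induction reading is always required.* Make-up readings may substitute.

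Finally, counting incomplete positives but not incomplete negatives makes entry to the denominator depend on the outcome. That is a fair criticism, so such a count should not stand alone.

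**Conclusion.** The gap is real but narrow. Under Section 4.3 as written, a diagnosed positive with a missing post-irradiation Challenge reading, or with fewer than 11 Induction evaluations, is not counted, and no other provision restores the case. With 50 other completers and no other positive, one such subject is the difference between 2.0% with an interval and 0% without one.

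The frequency is unknown, and the miss rates shown are assumptions. If missed readings were unrelated to reaction, the completer proportion would not be distorted on average, but an observed case would still be discarded. If reactions led to missed readings, the proportion would be pulled toward zero. The documents do not settle which applies, so they do not support a claim that the reported rate will be biased. They do support saying that it can omit a known case on the study's main question. This should be fixed, ideally before unblinding, but it does not invalidate the design.

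**What to change.** In Sections 4.3 and 4.6.2:

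1. Count as positive every subject who received the Challenge application and irradiation and whom the Investigator diagnoses as photosensitized at Challenge or Rechallenge, however many readings are available.
2. Keep the completeness rule for classing a subject negative.
3. Report three counts side by side: (a) positives over positives plus fully read negatives; (b) the strict-completer count as now defined; (c) positives over all subjects with at least one post-irradiation Challenge reading. Count (a) tilts slightly upward, because incomplete non-reactors stay out. Count (c) tilts slightly downward, because some of them might have reacted later. For one incomplete positive, 50 negative completers and one incomplete non-reactor, these are 1/51 = 2.0%, 0/50 and 1/52 = 1.9% (exact 95% CI 0.05% to 10.3%).
4. State whether Week 4 make-up readings count toward the 11, and reconcile Sections 3.1, 3.5.1, 3.5.7.1 and Table 2 on the readings in each phase.

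The cost is wording in the two statistical sections, the schedule reconciliation and a few table lines. No visits or subjects are added.
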